1.1 Study Title

Evaluation of Safety and Exploratory Efficacy of CARTISTEM[®], a Cell Therapy Product for Articular Cartilage Defects: A Phase I/IIa Clinical Trial in Patients with Focal, Full-thickness, Grade 3-4 Cartilage Defects of the Knee

1.2 Developmental Phase Phase I/IIa

2 Name and affiliation of principal or coordinating investigators

2.3 Name and Title of the Clinical Trial Pharmacist

CARTISTEM[®] consists of umbilical cord blood-derived mesenchymal stem cells (hUCB-MSC; main component) suspended in a transparent pale pink medium and sodium hyaluronate

CONFIDENTIAL: These all contents herein are the sole property of MEDIPOST Co., Ltd. Any reproduction or distribution of this document without the written consent of MEDIPOST Co., Ltd is prohibited. Copyright © 2017 MEDIPOST Co., Ltd.

(device) intended for cartilage regeneration in patients with cartilage defects or injuries. Unlike other conventional investigational products, the innate biological properties of the living cells in this product limit the shelf-life of the suspension (mixture of hUCB-MSC and HA) to less than 72 hours after preparation. Therefore, the investigational product needs to be delivered to the test site on the day of the actual surgery so that the on-site preparation and administration to the patient can take place shortly after receipt of the two vialed CARTISTEM[®] components (hUCB-MSC and lyophilized HA). Designation of a clinical trial pharmacist is deemed unnecessary as the unused portion of the investigational product which is ordered and administered on an individual subject basis is to be returned to MEDIPOST after the surgery. Therefore, a clinical nurse is given the role of managing the investigational product under supervision of the principal investigator and the subinvestigators.

Moreover, CARTISTEM[®] does not require a separate compounding or preparation process of a clinical trial pharmacist as the product can be mixed and used by the principal investigator in the surgery room. Hence, it was decided that it would be acceptable to have an appropriate individual designated by the (principal) investigator order, receive the shipment of, and return the investigational product to the sponsor. Therefore, a clinical nurse is assigned the role of managing the investigational product under the supervision of the investigator.

4.1 Cartilage defects

Chondral defects or damage to articular cartilage due to accidents, repetitive trauma or arthritis are common disorders. They are major causes of disability, as they can lead to osteoarthritis and they rarely heal spontaneously (e.g., Dragoo et al. 2003, Moore et al. 2005). As the population ages and as more young people participate in active sports, the size of the target patient group is also growing. However, despite ongoing research efforts, clinical products directed at cartilage repair remain limited.

Articular cartilage consists of hyaline cartilage and is a highly differentiated connective tissue covering joint surfaces. It is avascular and alymphatic, and it is sheltered from the immune system. It also has no nerve supply and is therefore not sensitive to early injuries. Articular cartilage also has poor repair properties because there are relatively few cells in the tissue, the metabolic rate is low, and the capacity of chondrocytes to divide and migrate within articular cartilage is restricted by the dense matrix. As a consequence, it is generally agreed that articular cartilage does not repair significantly after damage to the collagen matrix (e.g., Chang et al. 2006, Gelse et al. 2003, Hedrick and Daniels 2003, Katayama et al. 2004, Risbud et al. 2001, Wakitani et al. 2002). Therefore, damage to the tissue as a result of trauma generally progresses to osteoarthritis.

In most cases, the critical limiting step for the induction of spontaneous cartilaginous repair is incomplete and leads to the formation of fibrous, or at best fibrocartilage, tissue – a tissue intermediate of fibrous mesenchyme and cartilage, depending on the location and size of injury. Compared with the native hyaline articular cartilage, fibrous repair tissue has poor mechanical qualities and is prone to fail in the long term (Athanasiou et al. 2001, Chuma et al. 2004, Gelse et al. 2003, Guo et al. 2004, Mizuta et al. 2004, Moore et al. 2005, Otsuka et al. 1997). It is, CARTISTEM®

CONFIDENTIAL: These all contents herein are the sole property of MEDIPOST Co., Ltd. Any reproduction or distribution of this document without the written consent of MEDIPOST Co., Ltd is prohibited. Copyright © 2017 MEDIPOST Co., Ltd.

therefore, desirable to develop procedures that allow for improved repair of cartilage defects, as discussed below.

4.2 Investigational cellular-surgical combined interventions

Various different types of treatments are in use, such as drug therapy, arthroscopy, joint replacement surgery, marrow stimulation techniques (drilling, abrasion arthroplasty and microfracture for stimulation of local MSC), periosteal grafts, and autologous chondrocyte transplantation (Athanasiou et al. 2001, Risbud et al. 2001, Smith et al. 2005). However, conventional treatment modalities have not been able to provide complete and sustained resolution of symptoms following damage to the articular cartilage. Despite the numerous techniques available today, complete healing of damaged or defective cartilage or consistent reproduction of normal hyaline cartilage does not occur, and continuous drug administration or secondary surgeries are common. Thus, functional restoration of diseased and damaged human articular cartilage continues to remain one of the most challenging orthopedic problems and the clinical need for cartilage repair/regeneration technologies is undisputed (Athanasiou et al. 2001, Elisseeff 2004, Gelse et al. 2003, Lee et al. 2010, Smith et al. 2005, Yanai et al. 2005).

The latest attempts to develop clinically useful procedures for repairing damaged articular cartilage include the use of cells with the potential for cartilage repair. There are three potential cell types that may be utilized: chondrocytes (already used in the autologous chondrocyte transplantation technique), adult (somatic) stem cells and embryonic stem cells (Barry 2003, Browne et al. 2005, Giannoni et al. 2005, Guo et al. 2004, Otsuka et al. 1997, Yanai et al. 2005).

Chondrocyte implantation has long been considered as a potential treatment and several approaches of chondrocyte implantation are in current clinical use. Implantations of previously isolated and *in vitro* amplified autologous chondrocytes are being performed in current clinical practice. The disadvantages of this procedure are the limited proliferative capacity of adult chondrocytes, the issue of dedifferentiation in culture and required re-differentiation upon implantation, as well as the need for a 2-stage procedure for harvest and implantation.

The use of stem cells is the most recently developed and investigated method. The most promising approaches involve the introduction of MSC /cartilage precursor cells. Bone marrow

CONFIDENTIAL: These all contents herein are the sole property of MEDIPOST Co., Ltd. Any reproduction or distribution of this document without the written consent of MEDIPOST Co., Ltd is prohibited. Copyright © 2017 MEDIPOST Co., Ltd.

contains non-hematopoietic progenitor cells capable of differentiating into osteoblasts, chondrocytes and adipocytes; because those differentiated cells have mesodermal origin, their bone marrow progenitors have been designated MSC.

The umbilical cord blood is a source of hematopoietic stem cells and is used for hematopoietic stem cell transplantation in patients with diseases such as leukemia, aplastic anemia, and congenital immune deficiency that require allogeneic hematopoietic stem cell transplants. Over 5,000 cases of umbilical cord blood-derived hematopoietic stem cell transplantations have been conducted globally as of 2004, and transplant treatments using umbilical cord blood are expected to increase even further in the future. Umbilical cord blood is blood from the placenta and umbilical cord, which can be easily collected from the umbilical cord after childbirth, and therefore the collection poses no risk of harm to either the mother or the infant. Considering the present US birth rate of about 4,000,000 infants per year, umbilical cord blood is one of the most readily available and non-invasive sources of mesenchymal stem cells. The mesenchymal stem cell found in umbilical cord blood is characterized by its ability to self-replicate as well as its multipotency, or the capability to differentiate into cell lineages that compose bone, cartilage, bone marrow stroma, adipocytes, tendon, neurons, and various other tissues and organs.

Research in MSC has had a rapid acceleration over the past decade and MSC-based therapy has become one of the objects of investigation for a new branch of medicine termed regenerative medicine. This emerging technology shows great promise for producing transplantable cartilage constructs to restore the function of degenerated joints. However, current treatment options using MSC for articular cartilage repair/regeneration are still at an experimental stage of development. Studies with MSC were conducted in various animal models while currently only one clinical investigation and two case reports with MSC are available (e.g., Wakitani et al. 2002, Wakitani et al. 2010).

4.3 CARTISTEM[®] (MEDIPOST Cell Therapy Product)

CARTISTEM[®] is intended to be used as a single-dose cellular therapeutic agent for cartilage regeneration in human subjects with cartilage defects of the knee as a result of ageing, trauma or

CONFIDENTIAL: These all contents herein are the sole property of MEDIPOST Co., Ltd. Any reproduction or distribution of this document without the written consent of MEDIPOST Co., Ltd is prohibited. Copyright © 2017 MEDIPOST Co., Ltd.

degenerative diseases.

The CARTISTEM[®] drug product consists of a combination of human umbilical cord bloodderived mesenchymal stem cells (hUCB-MSC; supplied as a liquid suspension) and lyophilized sodium hyaluronate, provided in separate vials for mixing prior to administration. The packaged drug product will be shipped and stored as two vials, one vial containing approximately 7.5x10⁶ hUCB-MSCs suspended in 1.5 mL medium (alpha-MEM) to be mixed with one vial containing 60 mg sodium hyaluronate (lyophilized). Upon admixture of the two vials, i.e. after distribution of the cells in the hyaluronate polymer, the reconstituted product (5x10⁶ cells/mL; 40 mg/mL sodium hyaluronate) is formed as a viscous gel which is implanted into the cartilage lesion during open surgery. The initial proposed clinical dose is to be 0.5 mL/cm² (approximately 2.5x10⁶ cells and 20 mg HA/cm²). Immune phenotype tests using flow cytometer demonstrated that the hUCB-MSCs are CD45 negative, CD14 negative, HLA-DR negative, CD29 positive, CD73 positive, CD105 positive, and CD166 positive.

hUCB-MSCs, the active ingredient in CARTISTEM[®], are expected to induce the regeneration of damaged cartilage tissues by repair of the microenvironment with paracrine effects or by differentiation towards tissue-specific pathways. Sodium hyaluronate is believed to function as a medical device to provide mechanical stability to the hUCB-MSC suspension, enabling the cells to remain at the site of the implantation and not disseminate into adjacent areas.

4.4 Sodium Hyaluronate

Hyaluronic acid is a natural component of the extracellular matrix in cartilage. The glycosaminoglycan is highly conserved and is widely distributed in the body. hUCB-MSCs express cell surface receptors (CD44) that bind to hyaluronic acid. Interaction between cells and the extracellular matrix regulates many biological processes that are important to cartilage homeostasis and repair, including cell attachment, growth, differentiation, and survival (Marcacci et al. 2005, Risbud et al. 2001).

Since the 1970's, hyaluronic acid has been clinically used as a chondroprotective agent (Caplan and Dennis 2006, Watterson and Esdaile 2000). In addition, sodium hyaluronate has been

CONFIDENTIAL: These all contents herein are the sole property of MEDIPOST Co., Ltd. Any reproduction or distribution of this document without the written consent of MEDIPOST Co., Ltd is prohibited. Copyright © 2017 MEDIPOST Co., Ltd.

FDA approved for the treatment of osteoarthritis of the knee since 1997 (as an orthopedic device – e.g. ORTHOVISC[®] High Mol, SUPARTZ[®] Dispo, SYNVISC[®] (Hylan G-F 20) and HYALGAN[®]). In 2003, HA was approved for injection into the mid to deep dermis for correction of moderate to severe facial wrinkles and folds (such as nasolabial folds). In all cases, the FDA has regulated the products as medical devices.

The sodium hyaluronate in the CARTISTEM[®] product is believed to provide a stabilizing function to the MSC enabling them to remain at the site of the implant and not spill over into adjacent areas. In fact, sodium hyaluronate (and its derivatives) has proven to be an ideal molecule for use in the delivery of cellular therapies such as autologous chondrocytes or MSC in cartilage repair helping to keep the implanted cells in place (e.g., Elisseeff 2004, Marcacci et al. 2005, Risbud et al. 2001). In addition, hyaluronic acid has been shown to be both non-toxic and biocompatible (Kasahara et al. 2008). Thus, sodium hyaluronate was considered highly desirable for use as a scaffold in CARTISTEM[®]. There is currently no evidence that the presence of sodium hyaluronate contributes in any way to the inherent activity of the implanted MSC. Therefore, MEDIPOST considers the sodium hyaluronate to be a device in the final administered CARTISTEM[®].

5 Purpose of the Study

The primary objective of the proposed single-center phase I/IIa study is to evaluate the safety of CARTISTEM[®], an allogeneic-unrelated mesenchymal stem cell (hUCB-MSC) suspension mixed with sodium hyaluronate, at doses ranging from 0.5×10^7 to 2.25×10^7 hUCB-MSC in patients with articular cartilage defects that are equal or greater than 2cm².

The secondary objective of the study is to evaluate the efficacy (regeneration of defective cartilage and decrease of pain) of CARTISTEM[®].

CARTISTEM[®] will be administered, as a function of the defect size, at a cell density of 0.25×10^7 cells/cm² (0.5 mL/cm² with 0.5×10^7 hUCB-MSC/mL) directly into the articular cartilage defect by open surgery.

CARTISTEM®

page 18 of 137

CONFIDENTIAL: These all contents herein are the sole property of MEDIPOST Co., Ltd. Any reproduction or distribution of this document without the written consent of MEDIPOST Co., Ltd is prohibited. Copyright © 2017 MEDIPOST Co., Ltd.

A total of 12 patients, initially 6 patients with defect sizes of 2 to 5 cm² (Dosage A) followed by an additional 6 patients with defect sizes of above 5 cm² (Dosage B), will be enrolled sequentially in 2 groups in order to evaluate whether dose-limiting toxicity (DLT) is detected.

Each patient will undergo a 6-week screening period for eligibility and a 12-month follow-up observation period for both the primary (safety) and secondary (efficacy) endpoints of the study. There is an additional long term follow-up observation visit at 24 months. The estimated total duration of the study is approximately 24 months.

Prior to administration of CARTISTEM[®], the defect will undergo debridement, and following appropriate preparation, perforation of the subchondral plate.

CARTISTEM[®] is applied directly onto the entire defect site.

For use at the clinical site, CARTISTEM[®] will be provided as a cell suspension and lyophilized sodium hyaluronate in separate glass vials.

In terms of post-operative rehabilitation, patients will be started on a continuous passive motion (CPM) device on post-operative day 1 and refrain from high-impact activities such as running for 20 to 24 weeks.

6 Study Design

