CARTISTEM® PHASE I/IIa CLINICAL TRIAL PROTOCOL MP-0201-01

Version 3.2 Date: 15 March, 2017

CARTISTEM® PHASE I/IIa CLINICAL TRIAL PROTOCOL

CARTISTEM®

page 1 of 137

CONFIDENTIAL: These all contents herein are the sole property of MEDIPOST Co., Ltd. Any reproduction or distribution of this document without the written consent of MEDIPOST Co., Ltd is prohibited. Copyright © 2017 MEDIPOST Co., Ltd.

Name of Company Name of Product: Umbilical Cord Blo Ex vivo, Combined	Protocol #: MP-0201-01								
Protocol Title	Evaluation of Safety and Exploratory Efficacy of CARTISTEM [®] , a Cell Therapy Product for Articular Cartilage Defects: A Phase I/IIa Clinical Trial in Patients with Focal, Full-thickness Grade 3-4 Articular Cartilage Defects of the Knee								
Clinical Phase	Phase I/IIa								
Study Overview	dy Overview CARTISTEM [®] will be administered at doses ranging from 0.5×10 ⁷ to 2.25×10 ⁷ hUCB-MSC (0.25×10 ⁷ cells/cm ² ; 0.5 mL/cm ² with 0.5×10 ⁷ MSC/mL) to patients with focal, full-thickness, Grade 3-4 articular cartilage defects of ≥ 2cm ² in size. Safety: Patient safety will be assessed step-wise with increasing levels of total hUCB-MSC and HA exposure: a total of 12 patients will be enrolled and treated with CARTISTEM [®] to evaluate whether dose limiting toxicity (DLT) is detected. DLT is defined as toxicity or adverse event of Grade 3 or higher [80 points or higher for pain] in two or more events at the surgery site among swelling, tenderness, range of motion, and pain in any one visit. DLT is also defined as adverse drug reaction of Grade 3 or higher in the Common Toxicity Criteria Adverse Events (CTCAE), Version 4.0, with the exception of the following events and that they are unresolved for 7 consecutive days, despite medical interventions: ✓ Abnormal results in lab test (Acidosis, Hyponatremia, Hyperbilirubinemia, etc.) ✓ Abnormal results in lab test (Acidosis, Hyponatremia, Hyperbilirubinemia, etc.) ✓ Pain, defined as severe pain; limiting self-care ADL ✓ Pain, defined as severe pain; limiting self-care ADL								
	✓ Fever, defined as > 40.0 degrees C (> 104.0 d	degrees F) for > 24 hours							
	Initially, 6 patients with lesion sizes of 2-5 cm ² w (Dosage A); if dose limiting toxicity is not detect after administration, an additional 6 patients, with	ed during a 12 week period							

page 2 of 137

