CONFIDENTIAL: These all contents herein are the sole property of MEDIPOST Co., Ltd. Any reproduction or distribution of this document without the written consent of MEDIPOST Co., Ltd is prohibited. Copyright © 2017 MEDIPOST Co., Ltd.

Clinical Trial Material (CTM)	CARTISTEM [®] (human allogeneic-unrelated umbilical cord blood-derived mesenchymal stem cells, hUCB-MSC, and sodium hyaluronate) CARTISTEM [®] consists of approximately 7.5 x 10 ⁶ hUCB-MSC suspended in 1.5 mL medium in one vial, and 60 mg sodium hyaluronate provided as a lyophilized sponge form in a separate vial. The two vials are mixed at the surgical site. Upon admixture of the two vials, the combination forms a viscous gel, which is implanted into the articular cartilage defect.
Clinical Trial Material Dosage and Administration	CARTISTEM [®] will be administered into the articular cartilage defect by open surgery at a dose of 0.5 mL/cm ² based upon size of the defect. The CARTISTEM [®] dosage has been selected based on the results derived from nonclinical studies and prior human experience (see Investigator's Brochure for further information)
Surgical Technique	Before application of CARTISTEM [®] , unstable chondral fragments are debrided using a curet and stable shoulders of healthy surrounding cartilage are created. After adequate removal of the debris, multiple holes are created across the entire articular cartilage defect with a 2~3 mm drill bit spacing the holes approximately 3~5 mm apart. CARTISTEM [®] is applied onto the drilled holes first, and then throughout the entire cartilage defect.
Post-operative rehabilitation	Patients will be started on a continuous passive motion (CPM) device on post-operative day 1 with a range of motion of 0-30 degrees initially. This will be increased by 10 degrees per day as tolerated to a maximum of 0-90 degrees. Patients will undergo CPM treatment for 6 hours per day over 6 weeks. The patient will remain touch-down weight-bearing (TDWB) for 6 weeks, and then advance to full-weight bearing during the next 6 weeks (up to week 12). The patient will refrain from high-impact activities, such as running, during the subsequent 8 to 12 weeks (week $20 - 24$).
Reference Therapy	The study does not include a reference compound.

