6.2 Subject Selection Criteria

- 1) Inclusion Criteria
- A. Patients with an intended- to- treat single focal, full-thickness cartilage defect (ICRS [International Cartilage Repair Society] Grade 3 or 4) of the knee as a result of ageing,

CARTISTEM®

page 19 of 137

CONFIDENTIAL: These all contents herein are the sole property of MEDIPOST Co., Ltd. Any reproduction or distribution of this document without the written consent of MEDIPOST Co., Ltd is prohibited. Copyright © 2017 MEDIPOST Co., Ltd.

trauma, or degenerative diseases

- B. Age \geq 18 years old
- C. Size of the articular cartilage lesion is $\ge 2 \text{ cm}^2$
- D. Swelling, tenderness and active range of motion \leq Grade II
- E. Joint pain : 20-mm 60-mm on VAS (Visual Analog Scale) at the time of Screening
- F. Appropriate blood coagulation, kidney and liver function laboratory parameters:
 - ✓ PT(INR) < 1.5, APTT <1.5×control
 - ✓ Creatinine \leq 2.0 mg/dL, Albumin \leq trace in urine dipstick test
 - ✓ Bilirubin \leq 2.0 mg/dL, AST/ALT \leq 100 IU/L
- G. Ligament instability \leq Grade II
- H. Lower extremity alignment within 5 degrees of the neutral weight bearing axis
- I. No meniscal surgery within the past 3 months and more than 5mm of meniscal rim remaining
- J. Ability and willingness to fully participate in the post-operative rehabilitation program
- K. Subject is informed of the investigational nature of this study, voluntarily agrees to participate in the study, and signs an IRB-approved informed consent prior to performing any of the screening procedures
- L. Body Mass Index (BMI) \leq 35 kg/m²
- 2) Exclusion Criteria
- A. Patients that have been treated previously and are asymptomatic
- B. Avascular necrosis / osteonecrosis
- C. Autoimmune or inflammatory joint disease
- D. History of infection within the past 6 weeks
- E. Surgery or radiation therapy within the past 6 weeks
- F. Serious medical co-morbidities which would otherwise contraindicate surgery, as determined by the investigator
- G. Currently pregnant or nursing
- H. Psychotic diseases, epilepsy, or any history of such diseases

CARTISTEM®

page 20 of 137

CONFIDENTIAL: These all contents herein are the sole property of MEDIPOST Co., Ltd. Any reproduction or distribution of this document without the written consent of MEDIPOST Co., Ltd is prohibited. Copyright © 2017 MEDIPOST Co., Ltd.

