Support for the range of CARTISTEM[®] doses (0.5×10^7 cells to 2.25×10^7 cells) to be evaluated for safety and efficacy in this phase I/IIa study comes from both preclinical studies and clinical results in humans (comprised of a completed Phase I/II study in Korean patients with articular cartilage defects (N=7) and an ongoing Phase III study in Korean patients (N=50), as follows:

NOAELs for CARTISTEM[®] have been determined in the rat (Study No. B04001; NOAEL = $3x10^7$ cells per mL; > $1x10^7$ cells per cm²) and the rabbit (Study No. B04004; NOAEL = $1.5x10^7$ cells per mL; > $0.3x10^7$ cells per cm²); however, it is possible that the design of these studies did not allow for a proper assessment of the NOAEL due to limitations on the density of cells administered, and an overall very low toxicity of the hUCB-MSC in the species examined.

No treatment-related SAEs have been reported in seven patients who participated in a phase I/II Korean study and 50 patients currently enrolled in an ongoing phase III Korean study; all of these patients have received single administrations of 0.25×10^7 cells/cm² (0.5 ml/cm² with $0.5x10^7$ MSC/mL) up to a maximum of $2.25x10^7$ total MSC; this number of cells represents a much higher dose than the NOAEL ($10x10^7$ MSC per mL) derived from CARTISTEM® page 22 of 137

CONFIDENTIAL: These all contents herein are the sole property of MEDIPOST Co., Ltd. Any reproduction or distribution of this document without the written consent of MEDIPOST Co., Ltd is prohibited. Copyright © 2017 MEDIPOST Co., Ltd.

Study B04001 (GLP repeat-dose toxicology study in rats).

Based on these findings (for further discussion, please see the Investigator's Brochure), MEDIPOST has selected a single administration of CARTISTEM[®] at 0.25×10^7 cells/cm² (0.5 mL/cm² with 0.5×10^7 hUCB-MSC/mL), with both the volume and total number of hUCB-MSC administered to patients being a function of the defect size.

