6.5 Dose Escalation

This clinical trial will employ the following dose escalation scheme:

[figure not shown]
A total of 12-18 patients will be enrolled and treated with CARTISTEM[®] for dose limiting toxicity (DLT) evaluation. Initially, 6 patients with lesion sizes of $2 - 5 \text{ cm}^2$ will be assigned to Dosage A and treated with $0.5 - 1.25 \times 10^7$ MSCs; if dose limiting toxicity is not observed at the 3 month time point for the first clinical efficacy evaluation, then another 6 patients with lesion sizes of above 5 cm² will be assigned to Dosage B and treated with more than 1.25 x 10^7 MSCs for further safety evaluation. If a DLT occurs to one or two patients of the group treated with the dosage A, 3 more patients will be assigned to dosage A. If DLT happens to 3 of the patients who were treated with the dosage A or above, this study will be halted and the FDA and IRB will be notified. The Independent Data Monitoring Committee will perform a comprehensive review of safety (see Section 9.1).

CARTISTEM®

page 24 of 137

CONFIDENTIAL: These all contents herein are the sole property of MEDIPOST Co., Ltd. Any reproduction or distribution of this document without the written consent of MEDIPOST Co., Ltd is prohibited. Copyright © 2017 MEDIPOST Co., Ltd.

If no DLT occurs to any of the dosage A patients, another 6 patients with larger defect sizes will be enrolled and assigned to dosage B. In case of no DLT observed, a total of 12 patients will be enrolled for safety and efficacy evaluation. However, 18 patients could be enrolled if DLT occurs to two patients. If DLT occur 3 or more patients treated with Dosage B, this study will be halted and the FDA and IRB will be notified. The Independent Data Monitoring Committee will perform a comprehensive review of safety (see Section 9.1).

CARTISTEM®

page 25 of 137

CONFIDENTIAL: These all contents herein are the sole property of MEDIPOST Co., Ltd. Any reproduction or distribution of this document without the written consent of MEDIPOST Co., Ltd is prohibited. Copyright © 2017 MEDIPOST Co., Ltd.

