6.6 Definition of Maximum Permissible Dose and Method of Dose Escalation

Dose Limiting Toxicity (DLT): DLT is defined as toxicity or events of Grade 3 or higher (80 points or higher against pain) in two or more events at the surgery site among swelling, tenderness, range of motion, and pain in any one visit. DLT is also defined as adverse drug reaction of Grade 3 or higher in the Common Toxicity Criteria Adverse Events (CTCAE), Version 4.0, with the exception of the following events and that they are unresolved for 7 consecutive days, despite medical interventions:

- ✓ Abnormal results in lab test (Acidosis, Hyponatremia, Hyperbilirubinemia, etc.)
- ✓ Fatigue, defined as not relieved by rest; limiting self-care ADL
- ✓ Pain, defined as severe pain; limiting self-care ADL
- ✓ Headache, defined as severe pain in various parts of the head, limiting self-care ADL Fever, defined as > 40.0 degrees C (> 104.0 degrees F) for > 24 hours

Maximum Tolerated Dose (MTD): If DLT occurs in 2 or fewer patients at the Dosage B level, the MTD will be Dosage B. If DLT occurs in 3 or more patients treated with Dosage B then the MTD will be Dosage A. If DLT occurs in 3 patients treated with Dosage A then the MTD will not have been determined in this study design.

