- 7) MRI performed at Week 24 and Months 12 and 24 will also evaluate for tumorigenicity at focal lesion of the knee administration

CARTISTEM®

page 34 of 137

CONFIDENTIAL: These all contents herein are the sole property of MEDIPOST Co., Ltd. Any reproduction or distribution of this document without the written consent of MEDIPOST Co., Ltd is prohibited. Copyright © 2014 MEDIPOST Co., Ltd.

site.

- 8) Administration of the Investigational Product: 500 μ L/cm² of defect size
- 9) From baseline to Week 24, only subjective knee evaluation form must be filled in.
- 10) Use of NSAIDs must be discontinued for 6 weeks prior to treatment and may be resumed following the treatment. Use of NSAIDs and any other analgesics must be discontinued for 48 hours and 24 hours, respectively, prior to VAS evaluation at Weeks 4, 8, 12, and 24, and Months 12 and 24.
- 11) Patient may be allowed to take analgesics within 24 hours prior to VAS evaluation at Week 2.

The subject must visit the center on the scheduled visitation date ± 5 days for Weeks 2, 4, and 8; ± 7 days for Week 12, ± 14 days for Week 24 after the administration of the investigational product. For the long term follow-up patient assessment, the subject must visit the center on the scheduled visitation date ± 30 days at Months 12 and 24.

CARTISTEM®

page 35 of 137

CONFIDENTIAL: These all contents herein are the sole property of MEDIPOST Co., Ltd. Any reproduction or distribution of this document without the written consent of MEDIPOST Co., Ltd is prohibited. Copyright © 2014 MEDIPOST Co., Ltd.

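### The stated range of 0.5–2.25×10^7 cells fits only defects of 2–9 cm², but the dosing rules set no upper lesion size or dose, so an MTD of Dosage B would have no upper cell number.

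*Combined protocol and SAP*

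**What the plan says.** **Where the range is closed.** The Synopsis (Study Overview) says the product "will be administered at doses ranging from" 0.5×10^7 to 2.25×10^7 cells. Section 5 repeats this range in the primary objective, for "hUCB-MSC in patients with articular cartilage defects that are equal or greater than" 2 cm². The dose rationale (Section 6.4) gives the same range and reports that the Korean patients treated so far received the same density, "up to a maximum of $2.25x10^7$ total MSC".

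**Where the rule is open.**
- Section 6.2, inclusion C: "Size of the articular cartilage lesion is" at least 2 cm². No inclusion or exclusion criterion gives an upper size.
- Section 6.5: patients with lesions above 5 cm² "will be assigned to Dosage B and treated with more than" 1.25×10^7 cells. No upper figure follows.
- Section 6.4, dose chart: the last row is marked 9 cm²~, 4.5 mL~, 2.25×10^7 cells~ and 180 mg~.
- Section 8.2, note 8: "Administration of the Investigational Product: 500" µL per cm² of defect, with no maximum.
- Section 7.2.5: the dose is worked out from the defect measured after debridement.

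**What the trial will conclude.** Section 6.6: "If DLT occurs in 2 or fewer patients at the Dosage B level, the MTD will be Dosage B".

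**The concern.** The primary objective is safety over a stated dose range, and the Synopsis says exposure is stepped up by total cells and total hyaluronate. In such a trial the upper end of the range is a figure that later readers will use. Here the objective gives one upper end and the dosing rules give none.

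Two things are at stake. First, a site that follows the dosing rules for a large defect would go beyond both the range in the objective and the highest total human dose the protocol cites, and nothing in the text flags it. Second, the MTD is named by cohort label. Dosage B is bounded only from below, so a finding that the MTD is Dosage B would appear to cover total doses that no one in the trial received.

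**Working it through.** **Inputs.** Density 0.25×10^7 cells/cm², volume 0.5 mL/cm² (Section 5) and 20 mg hyaluronate/cm² (Section 4.3). One vial holds about 7.5×10^6 "hUCB-MSC suspended in 1.5 mL medium in one vial, and 60 mg sodium hyaluronate" in a second vial (Synopsis, Clinical Trial Material). Highest cited human total: 2.25×10^7 (Section 6.4).

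**Formulas.** Cells = 0.25×10^7 × area. Volume = 0.5 mL × area. Hyaluronate = 20 mg × area. Vials = volume / 1.5 mL, rounded up.

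**Reproducing the plan's figures.**
- 2 cm²: 0.25 × 2 = 0.5, so 0.5×10^7 cells, the stated lower end.
- 5 cm²: 0.25 × 5 = 1.25, so 1.25×10^7 cells, the top of Dosage A.
- Area at the stated upper end: 2.25 / 0.25 = 9 cm².
- At 9 cm²: 4.5 mL, 180 mg, 4.5 / 1.5 = 3 vials, and 3 × 7.5×10^6 = 2.25×10^7 cells.

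The stated range therefore matches 2–9 cm² exactly. The lower end is consistent with the eligibility criteria. The upper end is not, because eligibility continues past 9 cm².

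**Above 9 cm².** Each further cm² adds 0.25 / 2.25 = 11.1% of 2.25×10^7. The documents give no distribution of defect sizes, so the sizes below are assumptions.

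| Assumed size | Volume | Cells | Share of 2.25×10^7 | Hyaluronate | Vials |
|---|---|---|---|---|---|
| 10 cm² | 5.0 mL | 2.5×10^7 | 111% | 200 mg | 4 |
| 12 cm² | 6.0 mL | 3.0×10^7 | 133% | 240 mg | 4 |
| 15 cm² | 7.5 mL | 3.75×10^7 | 167% | 300 mg | 5 |

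Density is 0.25×10^7 cells/cm² in every row.

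**The MTD.** Suppose the largest defect treated in Dosage B were 7 cm² (assumed). The highest total given would be 0.25 × 7 = 1.75×10^7 cells, or 1.75 / 2.25 = 78% of the stated upper end. With two or fewer DLTs, Section 6.6 would still name Dosage B, and neither 1.75×10^7 nor any other cell number would be attached to it.

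**The case against.** **Density is the relevant dose, and it does not change.** Section 6.3 argues that animal limits should be converted to cells per cm² at the application site. Section 6.4 gives them as above 1×10^7 (rat) and above 0.3×10^7 (rabbit) cells/cm², both higher than the trial's 0.25×10^7. On that measure a 12 cm² defect gets the same local dose as a 2 cm² one. This stands, and it limits the concern. It does not remove it: the Synopsis escalates total exposure, the two cohorts differ in total dose and not in density, and Section 6.4 itself doubts that the animal studies allowed a proper assessment.

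**The stated range is itself the limit.** A total above 2.25×10^7 would fall outside the objective, and the investigator may exclude anyone judged unsuitable. This stands in part: the text is ambiguous and does not plainly authorise higher totals. But the closed range sits beside four open rules, and a site measuring and dosing at surgery would follow the rules.

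**The ~ may mean about.** It appears only in the last row and in all four columns of it. Since Dosage B is elsewhere given only a lower bound, and above is the more natural reading.

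**The MTD point is a matter of reporting.** Dosage B is a size band by design, and the implanted dose can be worked out from the measured size. That is fair. It is also why the remedy is so cheap.

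**Conclusion.** The mismatch is real and worth correcting. The stated range holds for 2–9 cm² only. For larger eligible defects the rules lead to totals above that range and above the highest cited human total, by 11% of 2.25×10^7 for each extra cm². The MTD label inherits the missing upper end. The size of any excess depends on assumed defect sizes, and its frequency cannot be computed. This rests on the visible text; the scheme figure in Section 6.5 is not shown.

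A reader might infer more, and the documents do not support it:
- *That 2.25×10^7 is a cap which the plan breaches.* It is stated as this study's range and as the maximum given in earlier patients, never as a limit on dosing.
- *That doses above 9 cm² are unsafe or wholly unsupported.* What is missing is cited human experience at those totals. The per-cm² animal limits still apply to them.
- *That a Dosage A patient who measures above 5 cm² after debridement exposes a gap in the escalation.* Section 6.5 ties Dosage A to treatment with 0.5–1.25×10^7 cells, so a patient given more does not meet its definition. With the scheme figure not shown, the absence of a rule cannot be established.

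**What to change.** Make range and rule agree, in one of two ways.

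1. *Preferred.* In the Synopsis, Section 5 and Section 6.4, restate the range as 0.5×10^7 cells and above, and say that totals over 2.25×10^7 have no cited human experience, although density is unchanged. The cost is that the cited human support looks slightly weaker.
2. *If the sponsor intends 2.25×10^7 as the limit.* Add an upper lesion size of 9 cm² to Sections 6.2, 6.4 and 6.5 and to note 8 in Section 8.2. The cost is a slightly narrower population. A size limit is better than holding the volume at 4.5 mL for a larger defect found at surgery, which would dilute the dose: 4.5 / 10 = 0.45 mL/cm² at 10 cm² (10% lower) and 4.5 / 12 = 0.375 mL/cm² at 12 cm² (25% lower).

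In either case, add to Section 6.6 that the MTD is reported with the highest total cell number actually implanted and tolerated, and not only as Dosage B. This is a change of wording and needs only the defect size and dose of each patient.
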